[name], DPM, MSCE, FACFAS, is a coinvestigator and statistician responsible for the completion of this research project. Moreover, [name] holds the primary responsibility for preparation of a report for submission to a journal for consideration for publication of the results of this study. Any investigator involved with this study is obligated to provide the sponsor with complete test results and all data derived from the study. Neither the complete results of this study, nor any part thereof, carried out under this protocol, nor any of the information provided by the sponsor for the purposes of performing the study, will be passed on to any third party without the consent of the study sponsor, with the exception of the final report, which is to be submitted to a peerreviewed scientific journal with the intent of publication. The choice of the journal to which the written manuscript will be submitted, remains with the PI and coinvestigator (DSM), who will discuss the matter with the coauthors of the report. The report will be authored by the PI and selected investigators, as determined by the PI, and in accordance with standard requirements for authorship. The study sponsor, Marlinz Pharma of Houston, TX, cannot prohibit or block submission of the manuscript of the final report, or its publication, except for a temporary embargo of \leq 3 months. The PI agrees to delay submission of the report for a period not to exceed three months, at the request of the sponsor, should the sponsor determine that a temporary embargo on submission of the report is in their best interest.

References

1. Elewski BE. The effect of toenail onychomycosis on patient quality of life. Int J Dermatol. 1997 October 01;36(10):754-6.

CONFIDENTIAL

6. Safer LF. Randomized double-blind comparison of short-term itraconazole and terbinafine therapy for toenail onychomycosis. Acta Derm Venereol. 2000 August 01;80(4):317-8.

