Number of Participants	Analyzing for the dichotomous outcome, either cured or not cured, using Fisher's exact test for independent groups (active topical nails solution alone versus placebo nail solution), in a prospective randomized fashion, expressing the alternative hypothesis as two proportions, at $\alpha = 0.05$, and $\beta = 0.80$, with the event rate in controls estimated to be 0.01 and the event rate in cases estimated to be 0.3, and using a 1:1 ratio of cases to controls, 29 participants will be needed in each treatment group in order to identify a statistically significant difference, should one exist. In anticipation of dropouts, limited site enrollment, and center effects and multiple center effects (≥6 clinical sites), an additional 20% will be added in an effort to ensure statistical power. Therefore, a minimum of 70 participants will be enrolled and randomized, subject to the data safety monitor's surveillance and recommendation.
Diagnosis and Main Inclusion Criteria	The main clinical disease under evaluation is toe onychomycosis. Participants will be males and non-pregnant females 18 years of age or older that have been diagnosed with distal subungual onychomycosis (DSO) involving at least one toenail. Diagnosis of this condition is to be made on the basis of history, physical examination, and a mycological inspection that includes a tissue examination for fungal hyphae (PAS stain). Evidence of fungal hyphae will be considered a positive confirmation of the diagnosis of toenail onychomycosis.
Study Product and Regimen	All participants will be randomized to either the active topical nail solution group, antifungal solution treatment, or to the placebo nail solution group. The topical antifungal medication under investigation is Tolcylen [™] . It will be provided by Marlinz Pharma, Houston, TX, the study funding Sponsor. The topical therapy will be applied in accordance with the existing FDA-approved method for use of this cosmetic agent.
Duration of administration	Administration of the interventions, active and placebo, will continue for no longer than nine (9) months. Administration of the topical agent may stop sooner if clinical and mycological evidence of cures are identified prior to nine (9) months.

CONFIDENTIAL

ponson marine i narina	

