Efficacy of Topical Active Nail Solution versus Placebo Nail Solution Alone Principal Investigator: [name], DPM Sponsor: Marlinz Pharma

forms of onychopathy that mimic mycotic nail changes include psoriasis, mechanically-induced onycholysis, lichen planus, chronic paronychia, alopecia areata, subungual hemorrhage, dysvascular or post-traumatic onychogryphosis, aging, median canalicular dystrophy (pterygium), pincer nail, yellow nail syndrome, subungual melanoma, and subungual squamous cell carcinoma (30). Because it is often difficult to clinically distinguish between nail changes caused by fungal infection and those caused by nonfungal etiologies of nail dystrophy, it is recommended that nail plate and bed tissue fragments be obtained for mycological assessment in an effort to avoid over treatment with topical or systemic antifungal medications (9,31). Interestingly, 28.57% of clinical estimates were incorrect when experienced clinicians made a diagnosis of onychomycosis based solely on their clinical inspection and historical interview, when mycological lab testing was used to ascertain the actual presence of fungal hyphae in toenail fragments (13). It has also been shown that specimens obtained from the deep layers of the nail plate, subungual debris, and nail bed convey different rates of fungal confirmation, with the highest likelihood of confirming the presence of dermatophytes, non-dermatophyte molds, and yeast, coming from samples of the subungual debris (32).

Microscopic inspection of skin and nail scrapings that have undergone potassium hydroxide (KOH) dissolution of keratin is a reliable and simple, as well as relatively inexpensive, technique for rapidly identifying the presence of fungal hyphae. In-office Dermatophyte Test Medium (DTM), on the other hand, is understood to be an unreliable method when compared with independent mycology lab testing. One report describing 100 cases of suspected onychomycosis revealed a positive DTM result in only 50% of cases that displayed positive growth with fungal culture (33). Periodic acid-Schiff (PAS) staining of tissue specimens has been shown to be the most sensitive test when compared to KOH and culture results, with a sensitivity ranging from 61% to 98% (34).

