Topical antifungals are generally recommended for the treatment of distal and lateral subungual onychomycosis with less than 50% of the visible nail plate surface area without matrix involvement, < 2-mm nail plate thickness, and ≤ 4 nails involved (39,40). FDA-approved topical agents that have shown efficacy for antifungal use include ciclopirox nail lacquer, efinaconazole, and tavaborole. According to the package insert for ciclopirox 8% nail lacquer, a complete cure was observed in 5.5% and 8.5% of cases, and the mycologic cure was 29% and 36% (41). Efinaconazole 10% solution had 17.8% and 15.2% complete cure incidences and 55.2% and 53.4% incidences of mycological cure; and tavaborole displayed 6.5% and 9.1% incidences of complete cure rate and 31.1% and 35.9% incidences of mycological cure (41-43). Interestingly, confirmatory mycology testing before treatment in not cost effective with terbinafine whereas it is with efinaconazole (9). Topical therapy can be relatively expensive, with average monthly supply costs of \$76.43 for ciclopirox, \$687.54 for efinaconazole, and \$1885.75 for tavaborole (44-46).

The Tolcylen[™] antifungal solution consists of tolnaftate as an active ingredient and undecylenic acid, lactic acid, propylene glycol and urea as delivery system ingredients. The patented low surface tension Tolcylen[™] Solution is the first product of its kind to combine FDA-approved antifungal medication with nail renewal, cosmetic and penetration enhancing ingredients. Tolnaftate, a thiocarbamate antifungal, blocks ergosterol biosynthesis, thus inhibiting fungal membrane formation (47). Tolnaftate has been used for superficial mycotic infection, such as tinea pedis due to Trichophyton rubrum, Trichophyton mentagrophytes, and Epidermophyton floccosum (48, 49). The delivery system ingredients in Tolcylen[™] also have antifungal properties, and they convey a cosmetic effect in that they improve nail appearance. In a multicenter, randomized, double-blind, placebo-controlled trial, a statistically significantly greater incidence of mycological cure was observed with a topical preparation of urea, propylene glycol and lactic acid compared to placebo; specifically, 27.2% vs. 10.4% placebo for ≤ 50% nail involvement, and 19.1% vs 7.0% placebo for 51-75% nail involvement, after 26 weeks of treatment for distal and lateral

CONFIDENTIAL

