In the event that a participant withdraws from the study prior to the termination of the designated follow-up period, every attempt will be made to inquire as to the rationale that the participant used in deciding to withdraw. Moreover, permission will be sought to collect at least survival (time to event) data. In light of the importance of complete follow-up, in relation to the integrity of the research study, the following steps will be taken prior to concluding that a participant is definitely lost to follow-up:

- 1. Three separate telephone calls on three separate days, each to the participant's home and place of work.
- 2. A letter sent to the participant's residence via certified mail, asking the individual to contact the study center to discuss their progress and participation in the study.
- 3. A telephone call to the participant's next of kin, to inquire as to the participant's whereabouts and participation in the study.

Statistical Plan

Power and Sample Size Determination

CONFIDENTIAL

Analyzing for the dichotomous outcome, either cured or not cured, using Fisher's exact test for independent groups (active topical nail solution and placebo), in a prospective randomized fashion, expressing the alternative hypothesis as two proportions, at $\alpha = 0.05$, and $\beta = 0.08$, with the event rate in controls as 0.01 and the that in cases as 0.3, and using a 1:1 ratio of cases to controls, we will need 29 participants in each treatment group, or 58 participants overall, to be able to detect a statistically significant difference between the treatment arms. In anticipation of dropouts, limited site enrollment and center effects and multiple center effects (6 clinical sites), an additional 20% will be added in an effort to ensure statistical power. Therefore, a total of 70 participants will be enrolled and randomized, subject to the data safety monitor's surveillance and recommendation.

Statistical Methods

The primary endpoint in this study is the mycological presence or absence of fungal hyphae in fragments of the index toenail as viewed on the microscopic PAS stain, following the application of active topical nail solution, or placebo nail solution, to participant's mycotic toenails.

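### The power statement gives two conflicting beta values and no sidedness, and it rests on an unsourced 1% placebo cure rate below the only placebo mycological cure rates the protocol cites

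*Protocol*

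**What the plan says.** The sample-size calculation appears twice in the protocol. Both versions use Fisher's exact test, alpha 0.05, 1:1 allocation, 1% cured on placebo against 30% on active (in the Study Summary, "with the event rate in controls estimated to be 0.01 and the event rate in cases estimated to be 0.3"), and 29 per arm. Both add 20% to reach 70 participants; the Study Summary calls this a minimum.

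- Study Summary, Number of Participants: "\beta = 0.80$, with the event rate in controls estimated to be 0.01".
- Statistical Plan, Power and Sample Size Determination: "\beta = 0.08$, with the event rate in controls as 0.01".

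Neither place says whether alpha is one- or two-sided, and neither gives a source for the 1%.

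Statistical Methods makes the primary endpoint mycological: whether hyphae are seen on PAS stain of the index toenail. The Review of the Literature describes a placebo-controlled trial of a topical containing urea, propylene glycol and lactic acid, all of which it also lists as delivery ingredients of the study product. Mycological cure there was "27.2% vs. 10.4% placebo" with up to half the nail involved, and 19.1% against 7.0% with 51-75% involved. The same section describes PAS staining "with a sensitivity ranging from 61% to 98" per cent.

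**The concern.** Read literally, beta of 0.80 is 20% power and beta of 0.08 is 92% power. One calculation cannot have both, so the reader cannot tell what power was designed or whether the primary test is one- or two-sided.

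The control rate matters more. With a rate near zero, a handful of cures on active is enough for significance, so power falls quickly as placebo cures appear. The 30% active rate is in line with the mycological cure the protocol reports for two approved topicals (ciclopirox 29% and 36%, tavaborole 31.1% and 35.9%). The 1% placebo rate has no comparable support. If placebo cure is nearer 7-10%, a non-significant result would say much less than the stated power implies.

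**Working it through.** **Inputs (all from the protocol).** Placebo 0.01, active 0.30, alpha 0.05, 1:1, Fisher's exact test, 29 per arm. Total 58 × 1.2 = 69.6, rounded to 70, or 35 per arm.

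**Step 1: reproduce 29 by formula.** Two-sided normal approximation with d = 0.29 and mean rate 0.155:

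n = [1.96·√(2·0.155·0.845) + z·√(0.01·0.99 + 0.30·0.70)]² / 0.29² = [1.003 + 0.469·z]² / 0.0841

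- 80% power (z = 0.842): 23.2, so 24. With continuity correction, (23.2/4)·[1 + √(1 + 4/(23.2·0.29))]² = 29.7, so 30.
- Literal beta 0.80, i.e. 20% power (z = -0.842): 4.4, so 5 (11 with correction).
- Literal beta 0.08, i.e. 92% power (z = 1.405): 32.8, so 33 (40 with correction).

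The stated 29 therefore sits beside the corrected 80%-power answer of 30.

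**Step 2: exact power at 29 per arm.** Power is the sum, over placebo counts, of P(that count) × P(active count large enough for p ≤ 0.05). Two-sided:

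| Placebo cures | Probability | Active cures needed | P(reached at 30%) | Product |
|---|---|---|---|---|
| 0 | 0.7472 | 6 | 0.9068 | 0.678 |
| 1 | 0.2189 | 8 | 0.6786 | 0.149 |
| 2 | 0.0310 | 9 | 0.5213 | 0.016 |
| 3 | 0.0028 | 11 | 0.2292 | 0.001 |

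The sum is 84.3%. By the same method, 27 per arm gives 79.3%, 28 gives 81.9%, 33 gives 91.2%, 34 gives 92.5% and 35 gives 93.5%. A one-sided test at 0.05 gives 91.9% at 29 per arm.

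So 29 meets an 80% target two-sided. Beta of 0.08 needs 34 per arm two-sided, or 29 one-sided.

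**Step 3: other rates.** Two-sided Fisher at 0.05, same enumeration. The 35-per-arm column is 70 participants with no dropout.

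| Active vs placebo | Source of the pair | 29 per arm | 35 per arm |
|---|---|---|---|
| 30% vs 1% | planning rates | 84.3% | 93.5% |
| 30% vs 7.0% | planned active, cited placebo | 49.5% | 62.5% |
| 30% vs 10.4% | planned active, cited placebo | 33.5% | 43.4% |
| 36% vs 7.0% | top cited ciclopirox rate, cited placebo | 69.9% | 81.1% |
| 36% vs 10.4% | top cited ciclopirox rate, cited placebo | 53.6% | 64.8% |
| 27.2% vs 10.4% | both arms of the cited trial | 24.8% | 33.2% |
| 19.1% vs 7.0% | both arms of the cited trial | 13.3% | 19.9% |

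**Step 4: imperfect PAS sensitivity (an assumption, shown as a range).** Suppose true clearance is 30% vs 1% and a still-infected nail tests negative with probability 1 − s. The observed rates are then 0.30 + 0.70(1 − s) and 0.01 + 0.99(1 − s).

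| s | Active vs placebo | Power, 35 per arm |
|---|---|---|
| 98% | 31.4% vs 3.0% | 88% |
| 95% | 33.5% vs 6.0% | 80% |
| 90% | 37.0% vs 10.9% | 66% |
| 61% | 57.3% vs 39.6% | 22% |

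The end values of s are the protocol's own; 95% and 90% are intermediate assumptions.

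**The case against.** **The sample size is not wrong for its rates.** A reader might infer from the two beta values that 29 per arm is an arithmetic error. The documents do not support that. If 0.80 is a power labelled as beta, 29 clears 80% two-sided. If 0.08 is meant literally, a one-sided test gives it at 29, and the protocol does not rule that test out. This objection stands: the fault is in the labels and the missing sidedness.

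**The cited placebo rates are not this trial's rates.** It is tempting to say that 7.0% and 10.4% contradict the 1%. They come from a different preparation over 26 weeks rather than 9 months, with a cure definition the protocol does not give. Placebo cure was lower in the more involved nails, and this trial admits up to 100% involvement, so a lower rate is possible. This also stands. What remains is that the protocol gives no reason for departing from the only placebo figures it reports.

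**PAS sensitivity sets no floor.** A reader might take 61-98% sensitivity to mean that at least 2% of infected nails must test negative. Those are diagnostic figures, whereas nails in the main comparison were already PAS-positive at baseline. One minus diagnostic sensitivity is not an established false-negative rate for them. It makes 1% look optimistic and does no more.

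**Raising only the placebo rate is one scenario among several.** False negatives would raise both arms, and an active rate of 36% restores power to 81% against 7%. This is why a range is needed rather than a single lower figure.

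**Conclusion.** The point holds in a limited form. The two beta values conflict and the sidedness is missing, so the power statement is wrong as written, although 29 per arm is adequate for an 80% target at 1% vs 30%. Two-sided, the power at those rates is 84% at 29 per arm and 94% at 35.

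The larger issue is how heavily that power depends on an unsourced 1%. With placebo at 7.0-10.4%, 70 participants give 63-43% against 30% active and 81-65% against 36%. At the cited trial's own pairs the figures are 33% and 20%. All assume a two-sided Fisher test at 0.05, equal arms and no dropout, and all borrow rates from preparations other than the study product.

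These figures do not show that the trial is underpowered. They show that its power is uncertain over a wide range that the protocol does not disclose. Nor does the protocol say how a null result would be interpreted, so no misreading can be attributed to the sponsor.

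**What to change.** 1. In both places, replace the beta value with one power and a stated sidedness. If two-sided 0.05 is intended: Fisher's exact test, 1% vs 30%, 84% power at 29 per arm and 94% at 35 per arm. If one-sided was intended, say so and give the matching power.
2. Give a source or reason for the 1% placebo rate on the PAS endpoint, or plan with a higher control rate.
3. State the power at 70 participants as a range, before dropout: 63% (30% vs 7%), 43% (30% vs 10.4%), 81% (36% vs 7%), 65% (36% vs 10.4%), and 33% and 20% for the cited pairs 27.2% vs 10.4% and 19.1% vs 7.0%.

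The change rewrites two paragraphs. It needs no added participants and no change to design or analysis; the only cost is a less favourable stated power.

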A Randomized, Controlled Trial to Determine the Efficacy of Active Topical Nail Solution versus Placebo Nail Solution for the Treatment of Pedal Onychomycosis

Funding Sponsor:	Marlinz Pharma [name] [contact]
Study Product:	Topical antifungal solution (Tolcylen™)
Protocol Number:	AFMC16
IND Number:	Not applicable
Date:	01/07/2019
Administrative Change:	12/11/2022, 02/20/2023

List of Abbreviations

AACFAS — Associate American College of Foot and Ankle Surgeons AE — adverse event

AE/SAE — adverse event/serious adverse event

AFMC — Ankle and Foot Medical Centers of the Delaware Valley

CITI — Collaborative Institutional Training Initiative (CITI Program)

COID — conflict of interest disclosure

COPD — chronic obstructive pulmonary disease

- CRF case report form
- DPM Doctor of Podiatric Medicine
- DSM data safety monitor

DSO — distal subungual onychomycosis

DTM — Dermatophyte Test Medium

EC/IRB — ethics committee/institutional review board

FACFAS — Fellow of the American College of Foot and Ankle Surgeons

FDA — Food and Drug Administration

HIPAA — Health Insurance Portability and Accountability Act of 1996

IRB — institutional review board

KOH — potassium hydroxide

MSCE — Master of Science in Clinical Epidemiology

OnyCOE-t[™] — Nail Specific Medical Outcomes Study

PAS — periodic acid-Schiff

QOL — quality of life

SAE — serious adverse event

VNPIS — visible nail plate involvement score

Study Summary

Title	A Randomized, Controlled Trial to Determine the Efficacy of Active Topical Nail Solution versus Placebo Nail Solution for the Treatment of Pedal Onychomycosis
Short Title	Topical Active Nail Solution versus Placebo
Protocol Number	AFMC16
Phase	This study is designed to compare the effects of active topical nail solution versus placebo nail solution in participants with pedal distal subungual onychomycosis (DSO).

CONFIDENTIAL

1	
Methodology	This is an interventional study comparing active topical nail solution versus placebo nail solution for the treatment of toenail fungal infection. All clinical and mycological examinations will be performed by blinded assessors; and baseline and post-treatment mycological and quality of life measurements will be analyzed in a single-subject paired fashion.
Study Duration	It is estimated that the duration of time necessary for the completion of this protocol (time from the start of screening to the last participant processed and finishing the study) will be 19 months.

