Reference therapy	Participants in the control group will apply a placebo topical solution to the involved toenail/s. Preparation of the placebo solution, dimethicone 5%, was undertaken with the aim of making it as close as possible to the active topical nail solution in terms of color and texture, and other physical characteristics. The placebo nail solution, like the active topical nail solution, meets the FDA's safe ingredient criteria for an over-the-counter topical agent. The placebo, like the active topical nail solution, will be supplied in three (3) 7.5 ml tubes with a controlled-release applicator mechanism that allows thin coat of the solution to be applied at a time, and the instructions for application specify that only thin coat of solution to be applied daily to under the leading edge, borders of the toenail and the entire surface of the toenail.
Statistical Methodology	All participants will be followed to the endpoint of the study, in accordance with the proposed timeline (see below). An intention to treat analysis will be used. Data analysis will entail descriptive statistical methods, including mean and standard deviation, or median and quartile, to describe demographic variables; as well as inferential statistical methods that will include two sample tests of the null hypothesis for differences between the two treatment groups both before and after active topical nail solution or placebo application, and for comparisons of pre-treatment and post-treatment results in single participants, for mycological tests and outcomes. The Wilcoxon rank sum (Mann Whitney) test for unpaired data will be used to identify differences between the two intervention groups both before and after active topical nail solution or placebo application, and the Wilcoxon signed rank test for paired data will be used for comparison of pre-treatment and post-treatment results in single participants, mycological tests, and the OnyCOE-t [™] and Visible Nail Plate Involvement Scores. Participants will be analyzed as randomized, and the last observation carried forward method will be used if a participant fails to complete the study protocol (lost to follow up for any cause, whether at-random or otherwise). The participants, as well as all observers and outcomes assessors, will be blind to

CONFIDENTIAL

Research Protocol

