Secondary endpoints are changes in the participants' toenail-related quality of life, as measured using the OnyCOE-t[™] quality of life questionnaire (56,57), and changes in the appearance of the index toenail as measured using the visible nail plate involvement score. Additional demographic exposure variables will also be collected and analyzed in order to describe the participants in the study. Specifically, the participant's age, sex, body mass index (BMI), comorbidities and medications, as well as the number of mycotic toe nails, the duration of onychomycosis based on the participant's history, the presence of pedal digital deformity (hammer toe, claw toe, if present), and any local or systemic complication/s that may arise during the course of the investigation.

All participants will be followed to the endpoint of the study, in accordance with the proposed timeline. The data will be considered based on type and distribution. An intention-to-treat analysis will be used, and it will entail descriptive statistical methods, including mean and standard deviation, or median and quartile, to describe demographic variables; as well as tests of the null hypothesis that will include 2-sample Student's *t*-tests, or Wilcoxon rank sum tests, for differences between the two study groups both before and after intervention, and paired *t*-tests, or Wilcoxon signed ranks tests, for comparison of pre- and post-treatment results in single participants, for continuous data, depending on the distribution of the data. The statistician will be blind to treatment allocation, which will be denoted as "A" or "B" until the results are computed, after which time the precise nature of the allocation will be revealed.

CONFIDENTIAL

Participant Population(s) for Analysis

The specific population to be included in this intention-to-treat analysis will be the all-randomized population (any participant randomized into the study, regardless of whether they underwent topical application of active topical nail solution or the placebo). This population will be subjected to primary and secondary endpoint analyses. For any participant lost to follow, their last observation will be carried forward for the subsequent evaluations in accordance with the study timeline.

Safety and Adverse Events

Definitions

Adverse Event

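### The protocol names conflicting tests for its binary primary endpoint: Fisher's exact test where the trial is sized, rank-sum and paired tests where the methods are described

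*Protocol*

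**What the plan says.** Four places in the protocol bear on how the primary endpoint is tested.

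- **Sample size** (Study Summary, Number of Participants; body, Power and Sample Size Determination, under Statistical Plan). Both begin "Analyzing for the dichotomous outcome, either cured or not cured, using Fisher's exact test for independent groups", and the body names the groups as active solution and placebo.
- **Study Summary, Methodology.** Here "baseline and post-treatment mycological and quality of life measurements will be analyzed in a single-subject paired fashion".
- **Study Summary, Statistical Methodology.** Two-sample tests between the arms are planned, in a sentence that closes on mycological tests and outcomes. The rank-sum test is then named for differences between the arms. After that, "the Wilcoxon signed rank test for paired data will be used for comparison of pre-treatment and post-treatment results in single participants, mycological tests", together with OnyCOE-t and VNPIS. Fisher's test is not mentioned.
- **Body, Statistical Methods.** The primary endpoint is the presence or absence of hyphae on PAS stain. The tests listed are t or rank-sum between arms, and paired t or signed-rank for pre/post "results in single participants, for continuous data, depending on the distribution of the data". No test for a binary outcome is listed.

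The Objectives and Research Question sections make the aim a comparison of active with placebo.

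**The concern.** Three different tests can be read as the analysis of one primary endpoint: Fisher's exact test, the rank-sum test and the signed-rank test. The protocol does not rank them. The only test tied by name to mycological results is the within-participant one. It asks whether results changed from baseline, not whether active solution did better than placebo.

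The plan expects few events (control rate 0.01), and with sparse tables the choice between Fisher and rank-sum can decide significance. If the choice is settled after the data are seen, the result can depend on it. This is not a detail left for an SAP to fill in: the protocol names tests, and they disagree with the one it is sized on.

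**Working it through.** **Inputs from the protocol.** Control rate 0.01, active rate 0.30, 1:1 allocation, alpha 0.05, 29 per arm, 58 in total, raised by 20% to 70 (35 per arm). Sidedness is not stated and is taken as two-sided. Cured is read as PAS-negative, because the PAS result is the declared primary endpoint.

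**Reproducing the plan's figure.** The two-sided, continuity-corrected formula for two proportions at 80% power gives 30 per arm, close to 29. Full enumeration of the two-sided Fisher test gives power 81.9% at 28 per arm, 84.3% at 29 and 93.5% at 35. Inflation: 58 × 1.2 = 69.6, rounded to 70. So 29 fits a between-arm Fisher test at 80% power. (The summary prints beta as 0.80 and the body as 0.08. Power of 0.92 would need 34 per arm by exact Fisher, so only power 0.80 fits. That is a separate correction.)

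**Fisher against rank-sum on a 0/1 result.** With ties, the rank-sum statistic reduces to z² = [(N − 1)/N] × Pearson χ².

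For 0 versus 5 of 29:
- Fisher: p = 2 × C(29,5)/C(58,5) = 2 × 118,755/4,582,116 = 0.052.
- Rank-sum: χ² = 58 × 145²/(29 × 29 × 5 × 53) = 5.472; z² = 5.472 × 57/58 = 5.377; z = 2.319; p = 0.020.

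| PAS-negative of 29, placebo vs active | Fisher p | Rank-sum p (tie-corrected) |
|---|---|---|
| 0 vs 4 | 0.112 | 0.040 |
| 0 vs 5 | 0.052 | 0.020 |
| 1 vs 6 | 0.102 | 0.046 |
| 1 vs 7 | 0.052 | 0.024 |

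**How often they disagree.** Enumeration at 29 and at 35 per arm shows that every table significant by Fisher is also significant by rank-sum. The difference in rejection probability is therefore the probability of disagreement.
- Design rates, 29 per arm: 95.9% − 84.3% = 11.6%.
- Design rates, 35 per arm: 98.4% − 93.5% = 4.9%.
- True rate 10% in both arms, 29 per arm: type I error is 0.0087 for Fisher and 0.0535 for rank-sum.

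**The paired test.** Among participants PAS-positive at baseline, a change can only be from positive to negative. The exact signed-rank test on 0/1 data then reduces to a sign test, with p = 2 × 0.5^k for k conversions.
- k = 5: p = 0.0625.
- k = 6: p = 0.031.

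The other arm does not enter the formula. With 6 of 35 converting in each arm, each paired test gives p = 0.031, while Fisher between the arms gives p = 1.0.

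**The case against.** The strongest reply is that the between-arm test is present. Several parts of it stand.

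- **A reader might infer that Fisher's test is planned nowhere.** The text does not support that. Power and Sample Size Determination sits under Statistical Plan and says the dichotomous outcome is analysed by Fisher. Only the two methods texts omit it.
- **A reader might infer that every other test is confined to continuous data.** That restriction appears only in the body. The summary plans two-sample tests in a sentence that can be read to cover mycological outcomes, and its rank-sum sentence carries no such limit. So the between-arm test is in conflict, not absent.
- **Six conversions is not a fixed threshold.** Diagnosis of Primary Outcome also allows some PAS-negative participants to be randomized, and the analysis population is everyone randomized. With one change from negative to positive, six conversions give a sign-test p of 0.125, seven give 0.070 and eight give 0.039. The 0.031 result holds only for participants who are PAS-positive at baseline.
- **A reader might infer a false efficacy claim at a rate well above 5%.** At the 10.4% placebo cure rate quoted in the literature review, a placebo arm of 35 reaches six conversions with probability 15.1%. That is not a type I error of the treatment comparison. If placebo results really turn negative, the pre/post null is false, and a significant change on placebo would weaken an efficacy claim. The figure also depends heavily on the rate: 3.3% at the other quoted placebo rate of 7.0%, and about one in a million at the protocol's own 0.01.
- **Nothing declares the paired test to be the primary analysis.** The stated aim and hypothesis are comparative.

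None of this removes the conflict. Reading the summary's rank-sum test as the mycology test gives a between-arm analysis, but not the one the trial is sized on.

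**Conclusion.** The concern holds as an internal contradiction that must be resolved before analysis. Fisher's exact test is the stated basis of the sample size, the summary offers rank-sum between arms and attaches mycology by name to a paired test, and the body's methods list nothing for a binary outcome.

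The choice matters at the margin of significance. The two between-arm tests fall on opposite sides of 0.05 for tables such as 0 versus 5 and 1 versus 6 of 29. At the design rates such disagreement has probability 11.6% at 29 per arm and 4.9% at 35. The paired test is a different matter, because it cannot answer the primary question whatever its p-value.

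These figures assume two-sided testing, cured meaning PAS-negative, the protocol's rates of 0.01 and 0.30, and a tie-corrected rank-sum test. The documents do not support the stronger conclusion that no valid between-arm analysis is planned, or that the plan carries a calculable excess false-positive rate through the paired test.

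**What to change.** In the Study Summary (Statistical Methodology) and the body (Statistical Methods):

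1. State one primary analysis: the proportion PAS-negative at the primary efficacy time point, active versus placebo, by two-sided Fisher exact test at 0.05.
2. State that any paired pre/post mycology result is descriptive and is not evidence of efficacy. Bring the paired-analysis sentence in the summary's Methodology entry into line. The paired summaries need not be deleted.
3. Limit the t and rank tests to VNPIS and OnyCOE-t.

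A site-stratified sensitivity analysis is optional; the protocol already says that center effects will be considered.

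The cost is a few sentences of text. Data collection and conduct are unaffected, and the sample size stands, with exact Fisher power of 84% at 29 per arm and 94% at 35.
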